7.7.3 Action on Study Drug

The number and percentage of patients for the following actions on study drug for MLN0128, exemestane, and fulvestrant:

- Dose Reduced at Least Once.
- Dose Held at Least Once.
- Dose Missed at Least Once.
- Discontinued Permanently.

Action on study drug will be summarized by cycle (cycles 1-6) and overall for the safety population.

7.8 Efficacy Analysis

Phase 1b

Data listings will present the tumor measurements from CT or MRI, the sum of the long diameter (SLD), percent change from baseline in the SLD, percent change from nadir in the SLD, non-target disease assessment, new lesion assessment, disease response assessment by the investigator based on RECIST criteria, and if symptomatic deterioration occurred at each response assessment. In addition, the best overall response (unconfirmed and confirmed), duration of stable disease (SD), and duration of response will be presented in a data listing.

See Section 7.8.3 Additional Efficacy Endpoints for the definition of duration of stable disease and the duration of response.

7.8.1 Primary Efficacy Endpoint(s)

Phase 2

The primary efficacy endpoint for the phase 2 portion of the study is the clinical benefit rate at 16 weeks (CBR-16) and is defined as the proportion of patients who achieve CR or partial response of any duration, or have stable disease [SD] at 16 weeks.

The number and percentage of patients achieving clinical benefit at 16 weeks will be summarized by cohort and combination partner (Exemestane or Fulvestrant) within each cohort. The estimate of the CBR-16 will be presented with a 2-sided 95% exact binomial confidence interval. CBR-16 will be determined based on both unconfirmed and confirmed response (see Section 7.8.3 Additional Efficacy Endpoints for definitions) for the response-evaluable population.

SD for at least 16 weeks is a subset of SD, only calculated for those patients with a best response of SD. It is defined as SD at the end of Cycle 2 and at the end of Cycle 4 (see exception below).

CBR at 16 weeks (unconfirmed) is defined as the number of patients who achieve CR or PR at any time or have SD for at least 16 weeks

CBR at 16 weeks (confirmed) is defined as the number of patients who achieve confirmed CR or confirmed PR at any time or have SD for at least 16 weeks or meet the following criteria:

Overall response at end of Cycle 2	Overall response at end of Cycle 4
CR/PR (unconfirmed)	SD
SD	CR/PR (unconfirmed)

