**Phase 2**

- To evaluate the antitumor activity by CBR at 16 weeks (CBR-16; defined as the proportion of patients who achieve CR or partial response of any duration or have SD at 16 weeks) of treatment with MLN0128 in combination with either exemestane or fulvestrant.

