7.8.2 Secondary Efficacy Endpoint(s)

Phase 2

Clinical benefit rate at 24 weeks (CBR-24)

The CBR-24 is defined as the proportion of patients who achieve CR or partial response of any duration, or have SD at 24 weeks.

The number and percentage of patients achieving CBR-24 will be summarized by cohort and combination partner (Exemestane or Fulvestrant) within each cohort. The estimate of the CBR-24 will be presented with a 2-sided 95% exact binomial confidence interval. The CBR-24 will be determined based on both unconfirmed and confirmed best overall response (see Section 7.8.3 Additional Efficacy Endpoints for definitions) for the response-evaluable population.

SD for at least 24 weeks is a subset of SD, only calculated for those patients with a best response of SD. It is defined as SD at the end of Cycle 2, Cycle 4, and Cycle 6 (see exception below).

CBR at 24 weeks (unconfirmed) is defined as the number of patients who achieve CR or PR at any time or have SD for at least 24 weeks.

CBR at 24 weeks (confirmed) is defined as the number of patients who achieve confirmed CR or confirmed PR at any time or have SD for at least 24 weeks or meet the following criteria:

Overall response at end of Cycle 2	Overall response at end of Cycle 4	Overall Response at the end of Cycle 6
CR/PR (unconfirmed)	SD	SD
SD	CR/PR (unconfirmed)	SD
SD	SD	CR/PR (unconfirmed)

Overall response rate (ORR)

The ORR is defined as the proportion of patients with a best response of CR or partial response. The number and percentage of patients achieving an ORR will be summarized by cohort and combination partner (Exemestane or Fulvestrant) within each cohort. The estimate of the ORR will be presented with a 2-sided 95% exact binomial confidence interval. The ORR will be determined based on both unconfirmed and confirmed best overall response (see Section 7.8.3 Additional Efficacy Endpoints for definitions) for the response-evaluable population.

Progression-free survival (PFS)

Progression-free survival is defined as the time from the date of first MLN0128 administration to the date of first documentation of disease progression or death due to any cause, whichever occurs first. Progression is based on the investigator response assessment per RECIST 1.1 criteria.

PFS in months is defined as:

(earliest date of progression or death – date of first dose of MLN0128 + 1)/30.4375

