In the event of progression, the date of progression is defined as the earliest date among target lesions, non-target and new lesions dates at that particular visit. For a patient whose disease has not progressed and is last known to be alive, PFS will be censored at the last response assessment that is SD or better.

The approach for handling of missing response assessments and censoring is presented in [Table 7.a](#).

Table 7.a Handling of Missing Response Assessment and Censoring

Situation	Date of Progression or Censoring	Outcome
No baseline tumor assessment	Randomization	Censored
No post baseline tumor assessment and no death	Randomization	Censored
Disease progression documented between scheduled visits	Date of first documented disease progression	Progressed
Disease progression documented subsequent to missing 2 or more adequate tumor assessments	Date of first documented disease progression	Progressed
No documented disease progression or no death	Date of last adequate assessment	Censored
Alternate subsequent therapy started prior to disease progression	Date of last adequate assessment prior to the start of subsequent therapy	Censored
Death without progression and without subsequent anti-cancer therapy	Date of death	Progressed
Adequate Assessment: investigator response assessment other than Unable to Assess, unknown or missing (i.e. CR, PR, SD or PD).		

PFS Analysis

The Kaplan-Meier method will be used to analyze the distribution of PFS for the Safety Population. Kaplan-Meier survival curves, the 25th, 50th (median), and 75th percentiles, along with associated 2-sided 95% confidence intervals (CIs) based on Brookmeyer and Crowley, and Kaplan-Meier estimates with 95% CIs at 6, 12 and 18 and 24 months will be presented.

The source of PFS (death or progressive disease) and the status of subjects who are censored in the PFS Kaplan-Meier analysis [no post baseline tumor assessment and no death, on-study (on treatment, in follow-up), Lost to follow-up, and received subsequent anti-cancer therapy] will be tabulated.

PFS will be summarized by cohort and combination partner (Exemestane or Fulvestrant) within each cohort.

Overall survival (OS)

Overall survival in months is defined as: (date of death – date of first dose of MLN0128 + 1) / 30.4375. Patients without documentation of death at the time of analysis will be censored at the

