7.12 Interim Analysis

There will be 3 interim analyses for futility in the Everolimus-Resistant Cohort and 2 interim analyses for futility in the Everolimus-Sensitive Cohort. The investigator-assessed CBR-16 rate will be used as the endpoint for the interim analysis. The interim analysis will be based on response-evaluable patients who have had the opportunity to complete a minimum of 4 cycles of treatment with MLN0128 or have discontinued treatment with MLN0128 before the end of Cycle 4.

In the Everolimus-Resistant Cohort, there will be 3 interim analyses based on the following assumptions:

- Ineffective CBR-16 rate (Ho): 10%.

- Effective CBR-16 rate (Ha): 20%.
- Alpha = 10%; power = 80%.
- Prior Beta Distribution Parameters: $a_0 = 0.10$, $b_0 = 0.90$.
- Probability of early termination under H_0 : 68%.

Timing of Interim Analyses in the Everolimus-Resistant Cohort

Stage	No. of Patients Evaluated	Number of Patients With CBR-16 to Proceed or Declare Active
1	29	≥ 3
2	39	≥ 4
3	49	≥ 6
Final	56	≥ 9

Abbreviations: CBR-16 = defined as the proportion of patients who achieve complete response or partial response of any duration, or stable disease) ≥ 16 weeks; No. = number.

In the Everolimus-Sensitive Cohort, there will be 2 interim analyses based on the following assumptions:

- Ineffective CBR-16 rate (H_0): 15%.
- Effective CBR-16 rate (Ha): 30%.
- Alpha = 5%; power = 80%.
- Prior Beta Distribution Parameters: $a_0 = 0.15$, $b_0 = 0.85$.
- Probability of early termination under H_0 : 71%.

Timing of Interim Analyses in the Everolimus-Sensitive Cohort

Stage	No. of Patients Evaluated	Number of Patients With CBR-16 to Proceed or Declare Active
1	23	≥ 4
2	38	≥ 7
Final	48	≥ 12

Abbreviations: CBR-16 = defined as the proportion of patients who achieve complete response or partial response of any duration, or stable disease) ≥ 16 weeks; No. = number.

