7.13 Changes in the Statistical Analysis Plan

The exemestane concentrations will not be summarized and exemestane PK parameters will not be estimated and/or reported due to the limited amount of PK evaluable data.

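### SAP 7.8.1 does not count a patient with SD at week 16 as a clinical benefit if her Cycle 2 scan is missing or not evaluable, although the protocol's CBR-16 asks only for SD at 16 weeks

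*SAP*

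**What the plan says.** Protocol 2.1 (Phase 2) defines CBR-16 as the "proportion of patients who achieve CR or partial response of any duration or have SD at 16 weeks". It sets no condition on any earlier scan. SAP 4.1 and the opening of SAP 7.8.1 give the same definition.

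SAP 7.8.1 then derives the SD component for patients whose best response is SD: "It is defined as SD at the end of Cycle 2 and at the end of Cycle 4 (see exception below". The exception is a two-row table, attached to the confirmed version only, that pairs SD at one of the two scans with an unconfirmed CR/PR at the other. No row covers a Cycle 2 result that is missing, not evaluable or unable to be assessed.

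SAP 7.8.2 repeats the construction for CBR-24 with three scans: "It is defined as SD at the end of Cycle 2, Cycle 4, and Cycle 6 (see exception below".

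For PFS, the SAP does plan for unusable scans. The note to Table 7.a reads "Adequate Assessment: investigator response assessment other than Unable to Assess, unknown or missing", and the table has rows for missed assessments. CBR-16 has no counterpart.

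SAP 7.13 lists a single change: "The exemestane concentrations will not be summarized and exemestane PK parameters will not be estimated and/or reported", because PK-evaluable data are limited.

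On versions, SAP 7.8.1 says "CBR-16 will be determined based on both unconfirmed and confirmed response". SAP 7.12 sets the cut-offs without naming one of them. Its table footnotes describe CBR-16 as the "proportion of patients who achieve complete response or partial response of any duration, or stable disease" of at least 16 weeks.

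**The concern.** The derivation is stricter than the endpoint it is meant to implement. A patient with no usable Cycle 2 scan, no progression and SD at Cycle 4 has SD at 16 weeks, yet she fails the two-scan condition.

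She also stays in the denominator. The response-evaluable population (Protocol 8.1.3, SAP 7.2.2) needs only one dose and measurable disease at baseline, and Protocol 8.1.4 rules out imputation, so the missing result cannot be filled in as SD.

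The effect runs one way: it can only lower CBR-16. Both cohorts are judged on counts at each interim and at the end, so each such patient removes one success from a go/no-go decision. The risk is stopping an active combination for futility, or declaring it not active.

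**Working it through.** **1. Which patients change status.** The schedule of events places scans at Cycle 2 Day 28 (week 8) and Cycle 4 Day 28 (4 × 28 = 112 days, week 16). Take Cycle 2 results of PR, SD or NE/missing and Cycle 4 results of PR, SD, NE or PD, with no response at any other time. That gives 12 pairs. The protocol definition and the SAP's unconfirmed version disagree on one:

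| Cycle 2 | Cycle 4 | Protocol | SAP unconfirmed | SAP confirmed |
|---|---|---|---|---|
| SD | SD | benefit | benefit | benefit |
| NE or missing | SD | benefit | **not benefit** | **not benefit** |
| NE or missing | PR | benefit | benefit | not benefit |
| SD | NE | not benefit | not benefit | not benefit |

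The confirmed version also loses some pairs with a single unconfirmed PR, such as the third row, but that comes from requiring confirmation. Progression at Cycle 2 ends benefit under either definition.

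**2. Reproducing the stated design.** Inputs are the boundaries in Protocol Tables 8-1 and 8-2 and SAP 7.12:

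- Resistant: ≥3/29, ≥4/39, ≥6/49, ≥9/56; H0 10%, Ha 20%.
- Sensitive: ≥4/23, ≥7/38, ≥12/48; H0 15%, Ha 30%.

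An exact binomial recursion through the stages gives:

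| Cohort | Alpha (stated) | Power (stated) | Early stop under H0 (stated) | Early stop under Ha |
|---|---|---|---|---|
| Resistant | 0.0982 (10%) | 0.8001 (80%) | 0.679 (68%) | 0.0853 |
| Sensitive | 0.0453 (5%) | 0.8029 (80%) | 0.713 (71%) | 0.0697 |

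The design reproduces, and power sits at its target with nothing to spare.

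**3. Effect of the two-scan rule.** Let *s* be the share of clinical benefit that rests on SD alone, and *m* the share of those patients whose Cycle 2 scan is unusable. The success rate the SAP would record under Ha is p1 × (1 − s × m). The documents give neither *s* nor *m*; the values below are assumptions. With s = 1 and m = 0.05, for example, the resistant rate is 0.20 × 0.95 = 0.19 and the sensitive rate 0.30 × 0.95 = 0.285.

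| s | m | Resistant: power | Resistant: early stop under Ha | Sensitive: power | Sensitive: early stop under Ha |
|---|---|---|---|---|---|
| none lost | 0 | 80.0% | 8.5% | 80.3% | 7.0% |
| 0.5 | 2% | 79.0% | 9.0% | 79.1% | 7.4% |
| 0.5 | 5% | 77.4% | 9.8% | 77.1% | 8.2% |
| 1 | 2% | 77.9% | 9.5% | 77.8% | 7.9% |
| 1 | 5% | 74.6% | 11.2% | 73.6% | 9.6% |

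For a given *m*, s = 1 is the upper bound of the loss. Type I error only falls: at s = 1 and m = 5% it is 0.0767 (resistant) and 0.0321 (sensitive).

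**4. One patient at the final boundary.** In the resistant cohort 9/56 (16.1%, exact 95% CI 7.6 to 28.3) is active and 8/56 (14.3%, 6.4 to 26.2) is not. In the sensitive cohort 12/48 (25.0%, 13.6 to 39.6) is active and 11/48 (22.9%, 12.0 to 37.3) is not.

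**5. CBR-24.** Either of two earlier scans can disqualify. If scan losses are independent, 1 − (1 − m)² of SD-benefit patients are exposed: 1 − 0.98² = 4.0% and 1 − 0.95² = 9.8%. This touches a secondary estimate only.

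**The case against.** **The SAP is silent on missing scans and never uses the word failure.** The outcome does have to be inferred, but from a stated rule: SD is required at both scans. The general denominator rule in SAP 7.1 (non-missing responses) could at most be read as dropping the patient. That is the less natural reading, because her Cycle 4 result is present and CBR-16 is specified for the response-evaluable population. She is not counted as a success on either reading.

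**SAP 7.12 carries its own footnote definition, with SD of at least 16 weeks and no two-scan condition, so the rule may not reach the cut-offs.** SAP 7.12 does not cross-refer to 7.8.1. But SD for at least 16 weeks is the very term that 7.8.1 defines by two scans, and no other derivation is offered. The SAP's own duration of SD (7.8.3) runs from Cycle 1 Day 1 to progression or the last assessment and needs no intermediate scan, so the duration idea does not justify the extra condition.

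**A patient who misses a scheduled assessment needs written permission to continue.** This note to the schedule of events limits missed scans. It does not cover scans that were done but could not be evaluated.

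**The expected loss is below one patient per cohort.** This stands. With all benefit SD, full enrolment and Ha true, it is 56 × 0.20 × 0.02 = 0.22 or, at 5%, 0.56 (resistant), and 48 × 0.30 × 0.02 = 0.29 or, at 5%, 0.72 (sensitive). The calculation also takes the Ha rates as free of this scan loss, which SAP 7.12 does not say.

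**Requiring both scans is a defensible conservative choice.** It cannot produce a false claim of activity, and with Cycle 2 unseen, change from nadir cannot be fully judged at Cycle 4. Both points are fair. A sponsor may choose the stricter rule, but it is then a different endpoint from the protocol's and should be declared.

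**Conclusion.** The concern holds. The SAP's derivation of the primary endpoint is narrower than the definition in the protocol and in the SAP itself, and the departure is not declared. It affects patients whose best response is SD, who have SD at Cycle 4 and whose Cycle 2 scan is missing or not evaluable.

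Their number is probably small. At assumed rates of 2% to 5%, power falls by about 1 to 5.5 percentage points in the resistant cohort and 1 to 7 in the sensitive cohort, depending on how much benefit is SD. In the worst of these cases, the chance of stopping an active regimen for futility rises from 8.5% to 11.2% (resistant) and from 7.0% to 9.6% (sensitive). The existence of the conflict does not depend on these assumptions; only its size does.

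The unnamed version of CBR-16 in SAP 7.12 is a lesser point. The footnote's reference to response of any duration points to the unconfirmed version. This should be corrected, but it does not undermine the design.

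**What to change.** - **SAP 7.8.1:** define SD at 16 weeks as SD at the end-of-Cycle-4 assessment with no earlier PD, and state that a missing or non-evaluable Cycle 2 scan does not disqualify the patient. The design then keeps its power of 80.0% and 80.3%.
- **SAP 7.8.2:** do the same for SD at 24 weeks, at the end of Cycle 6.
- **SAP 7.12:** state that the cut-offs apply to the unconfirmed version, with the confirmed version supportive.
- **If the two-scan rule is intended:** list it in SAP 7.13 as a change from the protocol endpoint and add a sensitivity analysis under the protocol definition.

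The cost is one sentence in each section and a small programming change, with no new scans, data or patients. The trade-off is that a patient whose Cycle 2 status was not seen is accepted as SD on her Cycle 4 scan alone, which the protocol wording already allows.

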7.8.2 Secondary Efficacy Endpoint(s)

Phase 2

Clinical benefit rate at 24 weeks (CBR-24)

The CBR-24 is defined as the proportion of patients who achieve CR or partial response of any duration, or have SD at 24 weeks.

The number and percentage of patients achieving CBR-24 will be summarized by cohort and combination partner (Exemestane or Fulvestrant) within each cohort. The estimate of the CBR-24 will be presented with a 2-sided 95% exact binomial confidence interval. The CBR-24 will be determined based on both unconfirmed and confirmed best overall response (see Section 7.8.3 Additional Efficacy Endpoints for definitions) for the response-evaluable population.

SD for at least 24 weeks is a subset of SD, only calculated for those patients with a best response of SD. It is defined as SD at the end of Cycle 2, Cycle 4, and Cycle 6 (see exception below).

CBR at 24 weeks (unconfirmed) is defined as the number of patients who achieve CR or PR at any time or have SD for at least 24 weeks.

CBR at 24 weeks (confirmed) is defined as the number of patients who achieve confirmed CR or confirmed PR at any time or have SD for at least 24 weeks or meet the following criteria:

Overall response at end of Cycle 2	Overall response at end of Cycle 4	Overall Response at the end of Cycle 6
CR/PR (unconfirmed)	SD	SD
SD	CR/PR (unconfirmed)	SD
SD	SD	CR/PR (unconfirmed)

Overall response rate (ORR)

The ORR is defined as the proportion of patients with a best response of CR or partial response. The number and percentage of patients achieving an ORR will be summarized by cohort and combination partner (Exemestane or Fulvestrant) within each cohort. The estimate of the ORR will be presented with a 2-sided 95% exact binomial confidence interval. The ORR will be determined based on both unconfirmed and confirmed best overall response (see Section 7.8.3 Additional Efficacy Endpoints for definitions) for the response-evaluable population.

Progression-free survival (PFS)

Progression-free survival is defined as the time from the date of first MLN0128 administration to the date of first documentation of disease progression or death due to any cause, whichever occurs first. Progression is based on the investigator response assessment per RECIST 1.1 criteria.

PFS in months is defined as:

(earliest date of progression or death – date of first dose of MLN0128 + 1)/30.4375

In the event of progression, the date of progression is defined as the earliest date among target lesions, non-target and new lesions dates at that particular visit. For a patient whose disease has not progressed and is last known to be alive, PFS will be censored at the last response assessment that is SD or better.

The approach for handling of missing response assessments and censoring is presented in [Table 7.a](#).

Table 7.a Handling of Missing Response Assessment and Censoring

Situation	Date of Progression or Censoring	Outcome
No baseline tumor assessment	Randomization	Censored
No post baseline tumor assessment and no death	Randomization	Censored
Disease progression documented between scheduled visits	Date of first documented disease progression	Progressed
Disease progression documented subsequent to missing 2 or more adequate tumor assessments	Date of first documented disease progression	Progressed
No documented disease progression or no death	Date of last adequate assessment	Censored
Alternate subsequent therapy started prior to disease progression	Date of last adequate assessment prior to the start of subsequent therapy	Censored
Death without progression and without subsequent anti-cancer therapy	Date of death	Progressed
Adequate Assessment: investigator response assessment other than Unable to Assess, unknown or missing (i.e. CR, PR, SD or PD).		

PFS Analysis

The Kaplan-Meier method will be used to analyze the distribution of PFS for the Safety Population. Kaplan-Meier survival curves, the 25th, 50th (median), and 75th percentiles, along with associated 2-sided 95% confidence intervals (CIs) based on Brookmeyer and Crowley, and Kaplan-Meier estimates with 95% CIs at 6, 12 and 18 and 24 months will be presented.

The source of PFS (death or progressive disease) and the status of subjects who are censored in the PFS Kaplan-Meier analysis [no post baseline tumor assessment and no death, on-study (on treatment, in follow-up), Lost to follow-up, and received subsequent anti-cancer therapy] will be tabulated.

PFS will be summarized by cohort and combination partner (Exemestane or Fulvestrant) within each cohort.

Overall survival (OS)

Overall survival in months is defined as: (date of death – date of first dose of MLN0128 + 1) / 30.4375. Patients without documentation of death at the time of analysis will be censored at the

date last known to be alive. The number and percentage of patients experiencing an event, the number and percentage of patients who are censored, the 25th, 50th (median), and 75th percentiles (and 95% CIs), and Kaplan-Meier estimates at 6 and 12 months (or other appropriate time points) will be presented for each cohort and combination partner.

OS will be summarized by cohort and combination partner (Exemestane or Fulvestrant) within each cohort.

Change in tumor size from baseline

Waterfall plots of the best percent of change from baseline in the sum of the longest diameter (SLD) of the target lesions will be generated for each cohort (legend for combination partner).

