- (d) Vital sign measurements include blood pressure (diastolic and systolic), heart rate, and temperature.
- (e) Single, 12-lead ECGs will be collected according to the schedule presented in the [Phase 1b Pharmacokinetic and ECG Sample Breakdown](#) and the [Phase 2 Pharmacokinetic and ECG Sample Breakdown](#) table. When the timing of an ECG coincides with blood samples for PK, the ECG should be completed first.
- (f) Contrast-enhanced imaging CT or MRI of the chest, abdomen, and pelvis must be obtained at baseline within 4 weeks before the first dose of MLN0128. Unless contraindicated, such contrast-enhanced imaging CT or MRI scans will be obtained every 2 cycles from Cycle 2 through Cycle 6 (ie, Cycle 2 Day 28, Cycle 4 Day 28, and Cycle 6 Day 28) and then every 3 cycles thereafter (ie, Cycle 9 Day 28, Cycle 12 Day 28, Cycle 15 Day 28, etc). A confirmatory scan should be performed at approximately 4 weeks from the previous scan for all patients with a complete or partial response. For those patients who have documented radiographic disease progression, CT or MRI scans are not required at the EOT visit. The same imaging modality (CT or MRI) should be used throughout the study.
- (g) After EOT, patients will be followed for PFS and OS; see Section 7.10 for more details. For those patients who discontinue MLN0128 for any reason other than radiographic disease progression, contrast-enhanced imaging CT or MRI scans should be completed to further assess disease progression (per RECIST, version 1.1).
- (h) Including serious pretreatment events; see Section 9.1.1.
- (i) Exemestane or fulvestrant should be administered according to the USPI or SmPC and according to the dose administered during previous treatment.
- (j) May be assessed up to 24 hours before the study visit.
- (k) For screening, creatinine clearance must be  $\geq 50$  mL/min based either on Cockcroft-Gault estimate or based on a 12- or 24-hour urine collection.
- (l) Coagulation assessment is required for all patients at times specified in the [Schedule of Events](#). When a tumor biopsy is required, coagulation assessment is required within 24 hours before obtaining the tumor biopsy. See Section 7.4.19 for additional information regarding tumor biopsy.
- (m) Fasting serum glucose will be measured in the clinic. Patients are required to fast overnight (nothing except water and/or medications after midnight or for a

	Screening (a)	TREATMENT CYCLES										EOT/ ET (b)	PFSFU /OSFU

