7.8.3 Additional Efficacy Endpoint(s)

Best Overall Response

Best Overall Response (unconfirmed): The best response after the first dose of study drug until subsequent therapy ordered from best to worst: Complete Response, Partial Response, Stable Disease, Progressive Disease. The best response can also be Unable to Assess, Unknown, or No assessment performed if this is the only investigator assessment of objective response available for the patient.

Best Overall Response (confirmed): The best response after the first dose of study drug until subsequent therapy ordered from best to worst: Complete Response, Partial Response, Stable Disease, Progressive Disease. The best response can also be Unable to Assess, Unknown, or No assessment performed if this is the only investigator assessment of objective response available for the patient.

Complete or partial responses may be claimed as best response only if the criteria for each are met at a subsequent time point. For the best overall response (confirmed), the confirmation derivation rules will be as described in the following table.

Confirmation Derivation Rules		
Overall response 1 st time point	Overall response subsequent time point	BEST overall response
CR	PR	PR
CR	SD	SD
CR	PD	SD
CR	NE	SD
PR	CR	PR
PR	PR	PR
PR	SD	SD
PR	PD	SD
PR	NE	SD
NE	NE	NE

Note: No adjustment for minimum criteria for SD is needed as the first protocol scan is at the end of cycle 2, approximately 8 weeks from first dose.

The number and percentage of patients in each response category (CR, PR, SD, SD-16, SD-24, Progressive Disease, Unable to Assess, Unknown, or no post baseline response assessment) will be summarized by cohort and combination partner (Exemestane or Fulvestrant) within each cohort.

Duration of Response (DOR)

The duration of objective response will be calculated for those patients with a best response of CR or PR, and is defined as the number of days from the start date of CR, or PR (whichever response is achieved first) until progressive disease or until the last response assessment if there is no progressive disease. For phase 2 the Kaplan-Meier method will be used to analyze the DOR. Kaplan-Meier survival curves, the 25th, 50th (median), and 75th percentiles, along with associated 2-sided 95% confidence intervals (CIs) based on Brookmeyer and Crowley will be presented.

Duration of Stable Disease

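### Read scan to scan, the confirmed CBR-24 rule (and, rarely, the confirmed CBR-16 rule) can fail a progression-free patient with two unconfirmed responses while passing one with stable disease throughout

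*SAP*

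**What the plan says.** SAP 7.8.1 and 7.8.2 derive CBR-16 and CBR-24 in an unconfirmed and a confirmed version, both for the response-evaluable population.

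- **Unconfirmed CBR-24:** "CBR at 24 weeks (unconfirmed) is defined as the number of patients who achieve CR or PR at any time", or who have SD for at least 24 weeks. Unconfirmed CBR-16 is built the same way.
- **Confirmed CBR-24:** "CBR at 24 weeks (confirmed) is defined as the number of patients who achieve confirmed CR or confirmed PR at any time", or who have SD for at least 24 weeks, or who match one of three rows. Writing R for an unconfirmed CR or PR at the ends of Cycles 2, 4 and 6, the rows are R/SD/SD, SD/R/SD and SD/SD/R.
- **SD for at least 24 weeks:** SD at all three cycle ends. The SAP adds: "SD for at least 24 weeks is a subset of SD, only calculated for those patients with a best response of SD".
- **Confirmed CBR-16:** "CBR at 16 weeks (confirmed) is defined as the number of patients who achieve confirmed CR or confirmed PR at any time", or who have SD at the ends of Cycles 2 and 4, or who match R/SD or SD/R.

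SAP 7.8.3 gives the confirmation rule: "Complete or partial responses may be claimed as best response only if the criteria for each are met at a subsequent time point". It then refers to a table that pairs a first time point with a subsequent one. PR then PR gives PR. PR then SD, and PR then NE, give SD.

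The protocol's Schedule of Events (footnote f) adds a scan: "A confirmatory scan should be performed at approximately 4 weeks from the previous scan for all patients with a complete or partial response".

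**The concern.** The exception rows have an evident purpose: a patient who responds but is not confirmed should keep the disease-control credit she would have had with SD. Every listed row allows for one unconfirmed response only. A patient with two of them, and no confirmed response, matches no clause. She would be counted as a failure although she never progressed and did at least as well at each cycle end as a patient with SD throughout, who is counted as a success.

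At stake are the ordering of patients within the confirmed rates, a small downward error in those rates, and reproducibility. Two programmers could classify the same record differently, and confirmed best response and confirmed ORR for that record depend on the same choice.

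**Working it through.** The plan states no figure for this point, so the check is to run the definitions over every possible record.

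**Inputs.** The CBR definitions and exception rows (SAP 7.8.1, 7.8.2), the confirmation sentence and table (SAP 7.8.3), and the confirmatory scan (protocol, Schedule of Events, footnote f).

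**Step 1: CBR-24, cycle-end scans only.** Each of three scans is CR, PR or SD without progression, so there are 3 × 3 × 3 = 27 sequences. Let R stand for CR or PR.

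| Cycles 2 / 4 / 6 | Sequences | Confirmed only by the next scan | Confirmed by any later scan |
|---|---|---|---|
| R/R/R | 8 | success (confirmed) | success (confirmed) |
| R/R/SD | 4 | success (confirmed) | success (confirmed) |
| SD/R/R | 4 | success (confirmed) | success (confirmed) |
| R/SD/SD | 2 | success (listed row) | success (listed row) |
| SD/R/SD | 2 | success (listed row) | success (listed row) |
| SD/SD/R | 2 | success (listed row) | success (listed row) |
| SD/SD/SD | 1 | success (SD) | success (SD) |
| **R/SD/R** | **4** | **failure** | success (confirmed) |

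Under the next-scan reading 4 of 27 sequences fail, all of the form R/SD/R. Under the any-later-scan reading none fail. The failure also requires that the Cycle 6 response is not confirmed afterwards. The same patient passes confirmed CBR-16 through its R/SD row.

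**Step 2: CBR-16, cycle-end scans only.** There are 3 × 3 = 9 sequences: R/R (4, confirmed), R/SD (2, listed), SD/R (2, listed) and SD/SD (1). None fail under either reading.

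**Step 3: add the four-week confirmatory scan.** Take PR at Cycle 2, SD or NE at the confirmatory scan, PR at Cycle 4, and no confirmation afterwards. Scan to scan, the first PR is followed by SD or NE and becomes SD; so does the second if its follow-up scan is not a response. The cycle ends now read R/R with neither response confirmed. That is not SD at both visits and not one of the two listed pairs, so she fails confirmed CBR-16. The same mechanism adds CBR-24 failures beyond R/SD/R, for example R/R/SD with an SD confirmatory scan after each response.

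**Step 4: size.** The documents give no frequency for these records. One affected patient moves a rate by 1/56 = 1.8 points (resistant cohort) or 1/48 = 2.1 points (sensitive cohort).

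As an illustration on assumptions that are not in the documents, suppose 10% of a cohort hovers at the PR threshold, so that each scan is independently PR or SD with probability 0.5, with no progression and follow-up ending at the confirmatory scan after Cycle 6. Read scan to scan, the chance that such a patient fails is:

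- CBR-24: 3 × 0.5^5 + 0.5^6 = 7/64. The three terms in 0.5^5 are two unconfirmed responses plus one SD; the last term is three unconfirmed responses.
- CBR-16: 0.5^4 × 0.75 = 3/64, where 0.75 is the chance of no confirmed response at Cycle 6.

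Per cohort:

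- Resistant (5.6 such patients): 5.6 × 7/64 = 0.6 for CBR-24; 5.6 × 3/64 = 0.3 for CBR-16.
- Sensitive (4.8 such patients): 4.8 × 7/64 = 0.5 for CBR-24; 4.8 × 3/64 = 0.2 for CBR-16.

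For CBR-24 in the resistant cohort, an assumed share of 5% gives 2.8 × 7/64 = 0.3 and 15% gives 8.4 × 7/64 = 0.9. The count stays below one while the share is under 1/(56 × 7/64) = 16%.

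These figures lean high. A tumour sitting exactly on the threshold is close to the worst case. Scans continue after Cycle 6, and under the same model each later scheduled scan confirms a response in 0.5 × 0.5 = 25% of those still unconfirmed.

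**The case against.** The strongest reply is that the SAP never says the confirming scan must be the next one. The sentence in 7.8.3 speaks of a subsequent time point, and so does the table's column heading. If the Cycle 2 PR is the first time point and the Cycle 6 PR a subsequent one, the PR/PR row applies, best response is ordered from best to worst, and R/SD/R is a confirmed success. A reader might infer that the sentence and the table contradict each other; the documents do not show that, because both can be read consistently. What stands is that the term is undefined. R/SD/R fits both the PR-then-SD row and the PR-then-PR row, and the SAP does not say which governs.

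Other stronger readings also fail:

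- **Two consecutive responses are scored as a failure.** They are not. PR directly followed by PR is confirmed in the 7.8.3 table.
- **The primary endpoint has a general hole.** It does not. At cycle-end scans no CBR-16 sequence fails; only the interim-scan case in Step 3 does.
- **The activity thresholds of 9 of 56 or 12 of 48 could turn on this.** No passage ties them to the confirmed version. Both documents define CBR-16 as counting a response whatever its duration, which matches the unconfirmed version, and that version cannot have this gap.

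It is also fair that both versions are reported, so any difference would be visible, and that one added row would close the gap at the cycle-end scans. That row alone would not cover the interim-scan cases.

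**Conclusion.** The point holds in a limited form. Confirmed CBR-24 has no row for R/SD/R. Under a scan-to-scan reading of the confirmation table, a progression-free patient with that record is a failure unless a later response is confirmed, while SD/SD/SD and R/SD/SD are successes. Confirmed CBR-16 and some further CBR-24 patterns are exposed only when the confirmatory scan is SD or NE and no response is ever confirmed.

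The error is always downward, touches the confirmed versions only, and is expected to be under one patient per cohort. That size rests on the assumptions in Step 4, not on trial data. If any later scan may confirm, there is no error at all, but the SAP leaves that open, and confirmed best response and confirmed ORR for the same record depend on it. This is a minor derivation defect worth correcting because the rule can rank a better-responding patient below a stable one.

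**What to change.** 1. In SAP 7.8.1 and 7.8.2, replace the exception rows for the confirmed versions with one rule. Besides confirmed CR or PR, count any patient without progression whose overall responses at the listed cycle ends (Cycles 2 and 4 for CBR-16; 2, 4 and 6 for CBR-24) are each SD or better, an unconfirmed CR or PR being treated as SD. At minimum, add the row CR/PR (unconfirmed), SD, CR/PR (unconfirmed) to the CBR-24 table.
2. In SAP 7.8.3, state whether a later, non-adjacent CR or PR before progression confirms the first one, and apply that rule to confirmed best response, ORR and CBR alike.

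Under the next-scan reading the first change takes the failing CBR-24 sequences from 4 of 27 to 0 of 27 and also closes the interim-scan case. It works whichever confirmation rule is chosen. The cost is a few lines of SAP text and programming, with no new data. The first change can only leave the confirmed CBR rates the same or raise them slightly.
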